5. STUDY ENDPOINTS

5.1 Primary endpoint

- The cumulative incidence of newly diagnosed hepatocellular carcinoma (HCC) at Week 240, the subject must meet one of the following criteria:
 - Without HCC before Week 24
 - A histological diagnosis of HCC (i.e. by biopsy or at post-mortem);
 - In patients with nodules > 2 cm, identification of typical HCC characteristics (hypervascular in the arterial phase with washout in the portal venous or delayed phases) by 4-phase multidetector CT scan or dynamic contrast-enhanced MRI;
 - In patients with nodules > 1 cm, identification of typical HCC characteristics by both techniques (4-phase multidetector CT and dynamic contrast-enhanced MRI).
- The cumulative incidence of disease progression at Week 240, defined as the first occurrence of any one of the following criteria:
 - An increase in Childs-Pugh score (as defined in Appendix 2) of 2 or more points from baseline;
 - An increase in Childs-Pugh score of 2 or more points, solely based on laboratory parameters (i.e. bilirubin, prothrombin time and/or albumin), confirmed between two consecutive visits at least one month apart;
 - Spontaneous bacterial peritonitis (with proven sepsis);
 - Renal insufficiency defined as a decrease in creatinine clearance to ≤ 50 mL/minute confirmed on two occasions at least one week apart (calculated from serum creatinine concentration);
 - Bleeding gastric/oesophageal varices;
 - Hepatocellular carcinoma;
 - Liver-related death.

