## Study Endpoints/Assessments

### Primary Endpoint

- Incidence of hepatocellular carcinoma at Week 240.
- Incidence of disease progression at Week 240, defined as the first occurrence of any one of the following criteria:
  - An increase in Childs-Pugh score (as defined in Appendix 1) of 2 or more points from baseline. an increase in Childs-Pugh score of 2 or more points, solely based on laboratory parameters (i.e. bilirubin, prothrombin time and/or albumin), confirmed between two consecutive visits at least one month apart;
  - spontaneous bacterial peritonitis (with proven sepsis);
  - renal insufficiency defined as a decrease in creatinine clearance rate to  $\leq 50$  mL/minute confirmed on two occasions at least one week apart (calculated from serum creatinine concentration, see section 11.2 Appendix 2);
  - bleeding gastric/oesophageal varices;
  - hepatocellular carcinoma;
  - liver-related death

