### 6.2.3. Clinical Endpoint

The cumulative incidence of disease progression during the study timepoints will be defined as the first occurrence of any one of the following criteria:

- an increase in Childs-Pugh score (as defined in section 11.1 Appendix 1) of 2 or more points from baseline.
- An increase in Childs-Pugh score of 2 or more points, solely based on laboratory parameters (i.e. bilirubin, prothrombin time and/or albumin), confirmed at two consecutive visits at least one month apart;
- spontaneous bacterial peritonitis (with proven sepsis);

- renal insufficiency defined as a decrease in creatinine clearance to  $\leq 50$  mL/minute confirmed on two occasions at least one week apart (calculated from serum creatinine concentration);
- bleeding gastric/oesophageal varices;
- hepatocellular carcinoma;
- liver-related death

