7.4.1 Analysis of primary variables

The primary efficacy endpoints for this study are the 240-Week cumulative incidence of newly diagnosed HCC and 240-Week cumulative incidence of disease progression. The newly diagnosed HCC is defined as HCC cases from Week 24 to Week 240. The analysis will be performed in mITT and PP population.

- Nominal cumulative incidence of newly diagnosed HCC at week 240 is defined as the percentage of patient who are newly diagnosed as HCC from Week 24 visit to Week 240 visit in overall patients. Nominal cumulative incidence of HCC will be summarized by frequency, percentage and its 95% two-sided Wald CI. When the value of the newly diagnosed HCC at week 240 is missing due to the epidemic of COVID-19, the missing value may be imputed with the value at the safety follow-up visit. Different missing imputation scenarios will be assessed for the primary analysis and sensitivity analyses, details are provided in below table in which “Y” means the missing value will be imputed with the value at the safety follow-up visit.

Difference between planned Week 240 visit and actual safety follow up visit	Medication taken after previous visit	Primary Endpoints	Sensitivity Analysis 1	Sensitivity Analysis2
<=28 days	Any	Y	Y	Y
>28 days	GSK	Y	N	Y
	Domestic	Y	N	N
	Both GSK & domestic	Y	N	N
Lost to follow up	NA	N	N	N

- Nominal cumulative incidence of disease progression at week 240 is defined as the percentage of patient who have disease progression before Week 240 visit in overall

patients. Nominal cumulative incidence of disease progression will be summarized by frequency, percentage and its 95% two-sided Wald CI. When the value of the disease progression at week 240 is missing due to the epidemic of COVID-19, the missing value will be imputed with the value at the safety follow-up visit. No sensitive analysis is planned.

- Cumulative incidence of newly diagnosed HCC/disease progression at week 240 and its 95% CI will be estimated from the Kaplan–Meier analysis. Time to newly diagnosed HCC/disease progression is defined as the interval between the date of first treatment dose and the analysis date. The rules of analysis date are described in the following table:

Patient's Condition	Status	Analysis date
Diagnosed HCC/disease progression on visit	Event	Date of diagnosis
Reported SAE related with HCC/disease progression between visits	Event	Date of diagnosis
Complete study without HCC/disease progression	Censor	Date of study complete

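### Disease progression (co-primary): an unconfirmed Child-Pugh rise of 2 or more points already counts on its own, so the confirmation rule for laboratory-only rises has no effect if both are measured from baseline

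*SAP*

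**What the plan says.** SAP 5.1 introduces disease progression as "defined as the first occurrence of any one of the following criteria". Protocol 6.2.3 uses the same combination rule. Both then give two Child-Pugh criteria as separate bullets:

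- **A.** SAP: "An increase in Childs-Pugh score (as defined in Appendix 2) of 2 or more points from baseline". Protocol: "an increase in Childs-Pugh score (as defined in section 11.1 Appendix 1) of 2 or more points from baseline". Neither asks for confirmation or limits the rise to clinical components.
- **B.** Protocol: "An increase in Childs-Pugh score of 2 or more points, solely based on laboratory parameters", with confirmation at two consecutive visits. The SAP has the same criterion, "solely based on laboratory parameters (i.e. bilirubin, prothrombin time and/or albumin), confirmed between two consecutive visits at least one month apart". Neither says what the rise is measured against.

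The renal criterion in the same list, which also rests on a laboratory value, must be "confirmed on two occasions at least one week apart".

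The Protocol Summary (Primary Endpoint) runs the two Child-Pugh sentences together in one bullet: "of 2 or more points from baseline. an increase in Childs-Pugh score of 2 or more points, solely based on laboratory parameters".

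The event table in SAP 7.4.1 has a row "Diagnosed HCC/disease progression on visit" and dates such events at diagnosis. It does not say whether progression is computed from the recorded scores or taken from the investigator, and it has no confirmation rule. SAP 7.4.2.2 applies the same event rules at Weeks 48, 96, 144 and 192.

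**The concern.** Clause B has a purpose only if a laboratory-only rise should not count until it is confirmed. Clause A has no such limit, and meeting either clause is enough. Read literally, a single abnormal set of bilirubin, prothrombin time or albumin results that moves the score by two points is a primary-endpoint event, even if the next visit is back at baseline.

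Compared with a rule that requires confirmation, the literal rule can only add events or date them earlier. Two analysts could also obtain different primary results from the same data, one letting A stand alone and the other treating B as a restriction on A. The choice affects the nominal percentage and the Kaplan-Meier estimate at Week 240, the earlier cumulative incidences, and the exploratory logistic and Cox models for progression.

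**Working it through.** **The plan's own figure.** The only design calculation concerns HCC. N = p(1 − p)(z/e)² = 0.05 × 0.95 × (1.96/0.034)² = 157.85, rounded up to 158. With 15% dropout, 158/0.85 = 185.9, rounded up to 186. These figures reproduce and do not depend on the Child-Pugh criteria. They matter here only for the denominator.

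**Is B contained in A?** Take both from baseline.

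1. B requires the Child-Pugh score to have risen by at least 2 points, through laboratory components alone, at two consecutive visits.
2. At the first of those visits the score is therefore at least 2 points above baseline. That is A.
3. Progression is dated at the first criterion met, so A fixes the event no later than the first of B's two visits. B adds no case and changes no date.

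A check by enumeration agrees. Let the laboratory part change by −2 to +6 points and the clinical part by 0 to +4 points at each of two visits: 9 × 9 × 5 × 5 = 2,025 patterns. B is met in 5 × 5 × 5 × 5 = 625, and none of these fails A at the first visit. Among the 81 patterns with no clinical change, 16 have no rise of 2 or more at either visit and 25 have one at both. The remaining 81 − 16 − 25 = 40 are unconfirmed laboratory-only rises that count through A alone. The redacted scoring table does not affect this argument.

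**If B has another reference point.** Measured from nadir, B could add a case. A score of 6 at baseline, then 5, then a confirmed 7 is +2 from nadir but +1 from baseline. An unconfirmed laboratory-only rise of 2 points from baseline would still count through A.

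**Weight of one event.** 1/186 = 0.54 percentage points of the nominal rate, if all 186 are in the mITT population.

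**Dating.** Visits are 12 weeks apart: 12 × 7 = 84 days. Each may move by 6 days either way from a date fixed from baseline (Protocol Table 1, footnote 2), so the gap runs from 84 − 12 = 72 to 84 + 12 = 96 days. A rise first seen at Week 48 and confirmed at Week 60 falls inside the Week 48 estimate if dated at the first visit, and outside it if dated at confirmation.

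**Opportunity to confirm.** There are 240/12 = 20 scheduled post-baseline visits. A first rise has a later scheduled treatment visit up to Week 228, that is at 19 of 20. One first seen at Week 240 does not.

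**Illustration only.** The documents give no rate of transient laboratory-only rises. Assume a chance q per visit, independent across 20 visits, in 186 subjects. Expected subjects counted without confirmation are 186 × [1 − (1 − q)²⁰]; the last column requires two consecutive visits.

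| q (assumed) | No confirmation | Two consecutive visits |
|---|---|---|
| 0.1% | 3.7 | 0.004 |
| 0.25% | 9.1 | 0.02 |
| 0.5% | 17.7 | 0.09 |
| 1% | 33.9 | 0.35 |

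Both q and the independence are assumptions, and the verdict does not rest on this table.

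**The case against.** The best reply is that this is loose drafting. B deals specifically with laboratory-only rises, so a sensible reader lets it govern them and leaves A for rises with a clinical component. The single bullet in the Protocol Summary fits that reading. That is probably what was meant, but it is not what two separate bullets under an any-one rule say, and a bullet break in the Summary may have been lost in text extraction.

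The event table speaks of diagnosed and reported events, so CRF instructions may already apply B. That cannot be checked. If it is so, the rule still belongs in the SAP. The remark in SAP 7.4.1 that no sensitivity analysis is planned for progression follows the COVID-19 imputation rule and says nothing about the definition. What stands is that the SAP offers no sensitivity analysis on the definition.

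Four limits also stand:

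- The number of affected subjects is unknown.
- The 84 days assume confirmation at a scheduled visit. An extra visit from one month onwards would shorten the gap.
- Protocol 4.4 says subjects who reach the primary endpoint will be withdrawn, while 3.1 says they may withdraw. A subject who leaves after a first rise may have no confirming visit, so 19 of 20 is an upper limit on opportunity. The two sections need reconciling.
- SAP Version 2.0 is dated February 2021 and already refers to Week 240 visits disrupted by COVID-19. Narrowing a primary endpoint that late in an open-label single-arm study could lower the reported rate after data have accrued.

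**Conclusion.** The point holds and should be fixed. As written, an unconfirmed laboratory-only Child-Pugh rise of 2 or more points from baseline is a co-primary event, whatever reference point B uses. If B is also measured from baseline, it is wholly contained in A and its confirmation requirement never operates. That second statement rests on an inference about B's reference point; the first does not.

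That confirmation was intended is inferred from the existence of B and from the confirmed renal criterion. The effect runs in one direction, towards more or earlier events, but its total size cannot be stated from the documents. The HCC endpoint's definition and the sample size are unaffected.

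**What to change.** **Definition.** In the Protocol Summary, Protocol 6.2.3 and SAP 5.1, replace the two bullets with one criterion: a Child-Pugh increase of at least 2 points over baseline, where an increase due only to bilirubin, prothrombin time and/or albumin counts only if it is present at two consecutive visits one month or more apart. This also supplies the reference point that B lacks.

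**SAP 7.4.1.** State:

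1. whether the event is derived from recorded scores or taken from the investigator's diagnosis;
2. which of the two visits dates a confirmed rise, for example the first;
3. how an unconfirmed laboratory-only rise is handled when it occurs at a subject's last visit, including a last visit caused by withdrawal.

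**Sensitivity analysis.** Report the progression count under the literal reading beside the primary count. Given the timing, record the reason for the choice before progression events are tabulated. Showing both counts lets readers see what the choice changed.

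**Cost.** Wording in three places, one derivation rule and one extra count. Chemistry and prothrombin time are scheduled at every visit, and Child-Pugh scores and progression events are already to be listed (Listings 4.5 and 4.1). Two uncertainties remain: Protocol Table 1 has no Child-Pugh row, and the documents do not say whether component scores are recorded, which are needed to identify a laboratory-only rise. The price of the narrower rule is that some genuine rises at a last visit may not count.

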5.2 Secondary endpoints

- Cumulative incidence of newly diagnosed HCC at Week 48, Week 96, Week 144, and Week 192.
- Cumulative incidence of disease progression at Week 48, Week 96, Week 144, and Week 192.
- The mean changes of liver stiffness measurement (LSM) at Week 12, Week 24, Week 36, Week 48, Week 96, Week 144, Week 192 and Week 240 for patients with baseline ALT > ULN,

baseline ALT \leq ULN and overall.

- Change of fibrosis stage for subjects with baseline ALT $>$ ULN and ALT \leq ULN.
- Change of non-invasive liver fibrosis evaluation index (GPR, APRI and FIB-4, defined in Section 8.5, appendix 5) from baseline by visit.
- The proportion of subjects with serum HBV DNA $<$ 20 IU/mL or serum HBV DNA $<$ 69 IU/mL (Roche COBAS Taqman HBV Test) at Week 12, Week 24, Week 36, Week 48, Week 96, Week 144, Week 192 and Week 240
- The mean \log_{10} IU/mL reduction in serum HBV DNA at Week 12, Week 24, Week 36, Week 48, Week 96, Week 144, Week 192 and Week 240 compared with baseline
- The proportion of subjects with ALT normalization at Week 48, Week 96, Week 144, Week 192 and Week 240 in subjects who have abnormal ALT at baseline
- For HBeAg positive subjects: the proportion of subjects achieving HBeAg loss, HBeAg seroconversion or HBsAg loss and HBsAg seroconversion at Week 24, Week 48, Week 96, Week 144, Week 192 and Week 240
- For HBeAg negative subjects: the proportion of subjects achieving HBsAg loss and HBsAg seroconversion at Week 48, Week 96, Week 144, Week 192 and Week 240
- Incidence of virological breakthrough as defined by 1 \log_{10} IU/mL increase in HBV DNA from nadir (as determined by two sequential HBV DNA measurements at least 1 month apart, or the last on-treatment measurement) overall and by each visit
- The proportion of subject with unsatisfactory response, overall and by each visit. Unsatisfactory response is defined as subjects who have HBV DNA \geq 200 IU/mL at week 48 and afterwards have \leq 1 \log_{10} IU/mL decrease in HBV DNA at two consecutive tests, confirmed by a third visit (additional visit) at least one month apart
- Subject safety as determined by adverse events and laboratory assessments

5.3 Exploratory endpoints

- Incidence of TDF resistance substitutions (if identified) at Week 48, Week 96, Week 144, Week 192 and Week 240
- Baseline or on-treatment risk factors for HCC/disease progression (e.g. gender, age, HBV DNA, genotype, HBeAg sero-status, ALT, platelets, treatment response, etc.)
- Impact of HBV DNA and virologic response on change of liver stiffness measurement (LSM).
- The mean changes of LSM by visit.

- Time to improvement of fibrosis.
- The Relationship between baseline variables or on-treatment variables and improvement of fibrosis.
- Proportion of LSM improvement and of fibrosis stage improvement.
- Analyses of correlation coefficients between LSM and ALT level.
- Correlation coefficients between variables change at Week 12 and 24 and LSM change at Week240.
- Predicted and observed HCC risks at week 240 by REACH-B model.
- Decline in LSM from baseline to Week 240.
- Mean estimated glomerular filtration rate (eGFR) over time by baseline eGFR, mean creatinine clearance rate (Ccr) over time by baseline Ccr, mean serum phosphorus over time.
- Change of average LSM/ALT by visit, change of average LSM by visit, change of median of LSM by visit, change of average GPR APRI FIB-4 by visit, change of median of GPR APRI FIB-4 by visit, change of fibrosis stage by visit.

6. STATISTICAL CONSIDERATIONS

6.1 General rule

All analysis will be conducted using SAS® Version 9.2 or higher (SAS Institute, Cary, NC). For continuous variables, descriptive statistics will be presented as the mean, standard deviation, minimum, median, maximum, and the number of observations, unless otherwise specified. For categorical variables, the number and percentage for each of the categories will be presented. Counts that are zero will be displayed as “0”. Unless otherwise specified, the denominator for all percentages will be based on the number of subjects in the analysis set of that treatment group. Baseline is defined as the last assessment before administration of the study drug.

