### 8.2. Study Design Considerations

#### 8.2.1. Sample Size Assumptions

Sample sizes are chosen based on feasibility and precision because no hypothesis is tested in this study.

The primary endpoint is the cumulative incidence of newly diagnosed as HCC in treatment group from Week 24 to Week 240.

To decide the number of subjects for analysis, some precision calculations have been performed. In the retrospective analysis of GS-US-174-0102 and GS-US-174-0103 trials, HCC incidence over 7 years was approximately 4.5% among patients (23% of whom were Asian, 25 of whom were genotype B or C) with cirrhosis at baseline. Accordingly, we hypothesize that the accumulative incidence of HCC at 240 weeks will be 5% in Chinese compensated cirrhotic patients treated with TDF. A sample size of 158 patients will allow us to estimate the confidence interval of the incidence with a margin of error at 3.4%( 0.016-0.084) Assuming a 15% drop out rate, 186 patients are to be recruited.

- Sample size formula:  $N = p(1 - p) \left(\frac{z_c}{e}\right)^2$

The main analyses will be performed on mdodified intent-to-treat (mITT) basis, including all patients who are assigned to treatment and received study medication. All endpoint analyses will use a last observation carried forward (LOCF) approach; that is, the last available visit is used as the end point. Changes from baseline to endpoint (LOCF) will be analyzed by Wilcoxon signed-rank test.

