### **8.3.5. Key Elements of Analysis Plan**

Missing data can have an impact upon the interpretation of the trial data. In general, values for missing data will not be imputed.

For the primary analysis of HCC incidence at Week 240, data from non-completers will use the last available visit as the end point.

All serum HBV DNA results below the lower limit of detection will be analysed as being the value of the lower limit of detection.

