4. ANALYSIS SET

- Modified Intent-to-treat (mITT) Population

The mITT population is defined as all recruited subjects who receive at least one dose of study medication.

- Per Protocol (PP) population

The PP population will consist of subjects in the mITT population who have no major protocol deviations that impact efficacy evaluation.

- Safety Analysis (SA) population

The SA population is defined as all subjects who receive at least one dose of study medication and have at least one post baseline safety assessment.

All efficacy endpoints will be analyzed using the mITT population and PP population will be used for primary endpoints. All safety endpoints will be analyzed using the SA population.

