6.2 Data handling

Missing data can have an impact upon the interpretation of the trial data. In general, values for missing data will not be imputed unless otherwise specified. For baseline value, if it is missing at baseline visit, then the latest non-missing value of screening will be used to replace.

All serum HBV DNA results below the lower limit of detection (<20 IU/mL) or results of “not detected” will be analyzed as being the value of the lower limit of quantification, which is 20 IU/mL. For patients whose week 240 visits were influenced by COVID-19, a safety follow-up were added for these subjects. The missing week 240 will be imputed from safety follow-up visit in the analysis of primary endpoints. Please refer to section 7.4 for details.

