7.4 Efficacy analysis

All analysis will be conducted in mITT, unless otherwise specified.

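### Several secondary response rates treat a missing visit as non-response without saying so, and COVID-missed Week 240 visits get no substitute value for them

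*SAP*

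**What the plan says.** SAP 6.1 sets the default, which applies where nothing else is specified: "the denominator for all percentages will be based on the number of subjects in the analysis set of that treatment group". SAP 7.4 adds: "All analysis will be conducted in mITT, unless otherwise specified". SAP 4 gives the set: "The mITT population is defined as all recruited subjects who receive at least one dose of study medication". No post-baseline result is needed to belong to it.

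On missing data, SAP 6.2 says that in general "values for missing data will not be imputed unless otherwise specified". For Week 240 visits disrupted by COVID-19 it makes one exception: "The missing week 240 will be imputed from safety follow-up visit in the analysis of primary endpoints". SAP 7.4.1 works this out for newly diagnosed HCC and disease progression only.

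SAP 7.4.2.3 asks for number, percentage and 95% CI for the secondary proportions. It restricts some by baseline status: ALT normalization to subjects with abnormal baseline ALT, serology to the HBeAg-positive or HBeAg-negative group. It restricts the two histology endpoints to paired biopsies. It names no denominator based on subjects assessed at a visit.

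The protocol has two rules. Section 8.2.1: "All endpoint analyses will use a last observation carried forward (LOCF) approach". Section 8.3.5: "In general, values for missing data will not be imputed", with use of the last available visit named only for the primary HCC analysis. The SAP contains no LOCF rule and does not mention the 8.2.1 sentence.

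**The concern.** No single sentence in the SAP says that a missing result is a failure. Combining the default denominator with the no-imputation default produces that rule for the virological, biochemical and serological response rates. The means are handled differently: SAP 6.1 summarises continuous variables with their number of observations, so the mean HBV DNA and LSM changes rest on those measured.

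Three things are at stake. First, Week 240 response rates mix drug effect with attendance, and the reader is not told. Second, Figures 4.5.1 and 4.5.1.1 plot HBV DNA response over time in mITT, so accumulating missing visits can look like waning suppression, while the mean HBV DNA plot (Figure 4.8.1.1) does not carry that effect. Third, subjects whose Week 240 visit was lost to the pandemic had a safety follow-up added, yet it cannot help these endpoints, even if the test was done there.

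The SAP also offers no second analysis to show the difference. It keeps the PP population for the primary endpoints only, and its COVID sensitivity analyses concern HCC.

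**Working it through.** **The plan's own figures.** With p = 0.05, z = 1.96 and half-width e = 0.034 (SAP 3.2.1), N = p(1 − p)(z/e)² = 0.05 × 0.95 × (1.96/0.034)² = 157.8, rounded up to 158. With 15% drop-out, 158/0.85 = 185.9, rounded up to 186. Both figures reproduce. They also supply the illustration: 186 dosed, 158 with Week 240 data, 28 without.

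**What the default denominator does.** If a share m of subjects has no result and a proportion r of those assessed respond, the observed-case rate is r and the default-denominator rate is r(1 − m). At 158 of 186 assessed, no reported rate can exceed 158/186 = 84.9%.

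**Illustration at Week 240.** The 90% response among those assessed is my assumption. The 15% is the planning figure, and the other two rows show a range. Differences use unrounded rates.

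| Without Week 240 data | Assessed | Responders | Observed-case | All mITT | Difference (points) |
|---|---|---|---|---|---|
| 5% | 177 | 159 | 89.8% | 85.5% | 4.3 |
| 15% | 158 | 142 | 89.9% | 76.3% | 13.5 |
| 25% | 140 | 126 | 90.0% | 67.7% | 22.3 |

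At 15% missing, assumed response between 70% and 95% gives a difference of 10.6 to 14.3 points. The Wald 95% CI for 142/186 is 70.2% to 82.5%, so the 89.9% seen in those assessed lies outside it.

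**Against LOCF.** If 50% to 100% of the 28 missing subjects were responders at their last visit (assumption), LOCF gives (142 + 14)/186 = 83.9% to (142 + 28)/186 = 91.4%.

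**Shape over time.** If losses accrue at a constant rate to 15% (assumption), the share remaining at Week 48 is 0.85^(48/240) = 0.968. The same 90% response would then be reported as 0.968 × 0.90 = 87.1% at Week 48 and 0.85 × 0.90 = 76.5% at Week 240, with no change among those assessed.

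**COVID-missed visits.** The documents give no count. At 186 subjects, each suppressed subject whose Week 240 visit is lost lowers the reported rate by 1/186 = 0.54 points.

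**Where the effect differs.**
- *ALT and serology:* the same formula applies within the baseline-defined group. For rare outcomes the absolute effect is small: 2% among those assessed (assumption) becomes 0.85 × 2% = 1.7%.
- *Breakthrough and unsatisfactory response:* the event is unfavourable, so a missed visit counts as no event. For example, 5/158 = 3.2% becomes 5/186 = 2.7%.
- *Histological improvement and cirrhosis reversal:* subjects without paired biopsies leave the denominator, so the default rule has no effect.

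**The case against.** The strongest reply is that missing-as-failure is a respectable conservative rule. Protocol 4.4 withdraws subjects after treatment interruptions of 28 days or more. Subjects who reach the primary endpoint are withdrawn or may withdraw, and SAP 7.1 lists lack of efficacy as a reason for discontinuation. Such subjects may well not be responders, and observed-case rates would leave them out. This stands, and it is why observed-case rates should not simply replace the default.

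A second reply is that the rule is inferred. SAP 6.1 allows exceptions, and the mock tables are in a separate document that might show a missing category or an assessed denominator. That is possible. But where the authors wanted another denominator (screening failures, all enrolled, abnormal baseline ALT, paired biopsies) they wrote it into the SAP, and they wrote none for subjects assessed at a visit.

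Third, the 15% is a planning figure. Protocol 4.4 asks for follow-up after study drug is stopped, so stopping treatment need not mean missing data. This also stands, and the range in the table allows for it.

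Fourth, the documents do not say that HBV DNA, serology or ALT was measured at the added safety follow-up, and the SAP's table foresees some subjects on domestic medication by then. Any substitution must be limited accordingly.

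A reader might also infer that the SAP breaches a clear LOCF requirement. The documents do not support that. The conflict lies inside the protocol, between 8.2.1 and 8.3.5, and the SAP follows 8.3.5.

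**Conclusion.** The point holds for HBV DNA below 20 and 69 IU/mL, ALT normalization, and HBeAg/HBsAg loss and seroconversion. As written, the SAP implies missing = non-response at each visit for these, without saying so, and COVID-missed Week 240 visits are counted the same way. With 15% of subjects lacking Week 240 data and 90% response among those assessed, the reported rate is 13.5 points below the observed-case rate. With 5% to 25% missing, the gap is 4.3 to 22.3 points. The response rate and the missing share are assumptions, and the pandemic's part cannot be computed from the documents.

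Two stronger readings are tempting and should not be drawn. One is that every missed visit in every secondary endpoint counts against the drug: breakthrough and unsatisfactory response are biased the other way, and the biopsy endpoints are not touched. The other is that a lower Week 240 rate would reflect attrition and COVID rather than loss of effect. The documents do not show what response the missing subjects would have had, and some reasons for leaving are related to poor outcome.

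The study is single-arm and descriptive, and the primary endpoints are not affected. The issue is how main secondary rates are reported and read. It should be settled in the SAP.

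**What to change.** 1. For Week 240 visits missed because of COVID-19, use the safety follow-up value for these secondary endpoints under the row of the SAP 7.4.1 table for a difference of 28 days or less, wherever the relevant test was done at that visit.
2. In the by-visit tables and in Figures 4.5.1 and 4.5.1.1, print the number assessed. Show two labelled rates side by side: observed-case and missing = failure. For breakthrough and unsatisfactory response, label the second as missing = no event. Do not rank observed-case as the main analysis.
3. State that the SAP follows protocol 8.3.5 and that the LOCF sentence in protocol 8.2.1 is superseded.

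The cost is SAP wording and extra table columns, with no new data collection. Observed-case rates favour subjects who stay in the study, and missing-as-failure rates fall with attendance. Neither is sufficient alone, which is why both are shown.
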